## KEY POINTS

- Conservative feeding therapies are thought to modify GERD symptoms and its consequences. However, in this randomized controlled trial in convalescing neonatal ICU infants with GERD symptoms, when controlling for preterm or full-term birth and severity of esophageal acid reflux index, the effectiveness of acid suppression plus a feeding modification bundle (volume restriction, intra- and post- prandial body positions, and prolonged feeding periods) vs. acid suppression alone, administered over a 4-week period was not superior in improving symptom scores or feeding outcomes.
- Restrictive feeding strategies are of no impact in modifying GERD symptoms or clinically meaningful outcomes. Further studies are needed to define true GERD and to identify effective therapies in modifying pathophysiology and outcomes.
- The improvement in symptoms and feeding outcomes over time irrespective of feeding modifications may suggest a maturational effect. This study justifies the use of placebo controlled randomized clinical trial among NICU infants with objectively defined GERD.

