short- and long-term clinical outcomes among infants treated concurrently over 4 weeks with PPI with randomly assigned feeding strategy modifications while controlling for gestational maturity (pre-term or full-term at birth) and severity of esophageal ARI (3-7%, >7%). Our *hypothesis* was that the study approach (acid suppression, modified feeding volume, duration, and position) was superior in achieving independent oral feeding or a 6-point reduction in I-GERQ-R vs the conventional (acid suppression alone) feeding approach.

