### **PARTICIPANT SELECTION, RANDOMIZATION AND ALLOCATION**

Inclusion criteria were: a) infants admitted with clinical symptoms of GERD between 34-60 weeks postmenstrual age, with physician's intent to treat with acid-suppressive therapy, b) an intake volume of full enteral feeds  $\geq 150$  mL/kg/day, c) room air or supplemental oxygen  $\leq 1$  liter per minute, and d) ARI  $\geq 3\%$  (6, 22-24). Exclusion criteria were: a) infants with known genetic, metabolic or syndromic diseases; b) neurological diseases including  $\geq$  grade III intraventricular hemorrhage or perinatal asphyxia, c) GI malformations or surgical GI conditions, and d) infants on acid suppressive medication at initial evaluation. Randomization was performed among consented subjects who were stratified 1:1 ratio by ARI severity (3%-7%: indeterminate acid reflux and  $>7\%$ : severe acid reflux) and by birth gestation (preterm, full term) into study feeding approach or conventional approach. Permuted Block Randomization with block sizes of 2, 4, 6, and 8 was undertaken by the study statistician (OSU Center for Biostatistics) using a computer-generated allocation and implemented in REDCap. Nurse coordinator enrolled subjects by verifying eligibility, obtaining parental consent, and entering demographic data into REDCap. PI and study staff who evaluated subject clinical outcomes were blinded to study allocation.

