## OUTCOME MEASURES

The *a priori primary end-point* was achieving independent oral feeds and/or a six-point decrease in I-GERQ-R score at 5 weeks or sooner, whichever was earliest at discharge. *To clarify further, there were 2 scenarios:* 1) Among infants who were transitioning to oral feeds (gavage fed) at inception: success was defined as achieving full oral feeds or a  $\geq 6$ -point decrease from baseline I-GERQ-R. 2) Among infants who were on full oral feeds at inception, success was determined if full oral feeds were maintained plus a  $\geq 6$ -points decrease from baseline I-GERQ-R. *Secondary end-points* included growth metrics (weight, length and head circumference), supplemental oxygen, economic metrics (LOHS), long-term feeding outcomes at 6 months and 1 year, and developmental outcomes at 2 years (32, 33).

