## STATISTICAL METHODS

Based on our preliminary data, we had planned to enroll 100 patients (50 per group) to detect 27% or higher increase in proportion of success of study group compared to the conventional group with 80% power and overall one-sided  $\alpha$  level of 0.025. One interim futility analysis was planned at about 50% information prior to the final analysis at 100% information, corresponding to 50 and 100 evaluable patients, respectively. The boundary was determined using Lan-DeMets spending functions to simulate O'Brein-Fleming boundaries(34). Using the target proportion of success, the boundary at the futility analysis was  $p>0.297$ .

Seventy-six infants were randomly assigned till the end of funding for this study and were included in the analysis of demographics and clinical characteristics (**Fig 1, Table 1**) and primary outcome by intent-to-treat. If a patient dropped out before the end of study and no symptom score was evaluable, we treated the patient as a failure for the primary outcome by intention-to-treat. Secondary outcome analysis was performed for 72 subjects (**Fig 1**). Futility boundary was not reached at interim analysis of 50 patients ( $p=0.1 < 0.297$ ) and accrual was continued with DSMB approval. Summary statistics were calculated for patient demographics and clinical characteristics for final analysis. Success rate in achieving PO or reduction in the I-GERQ-R by 6-points was calculated with 95% confidence interval and compared using chi-square test between the conventional and study groups (primary outcomes) for the intention-to-treat and treat-as-treated analyses. Fisher's exact or chi-square test were used to compare other categorical secondary outcomes including feeding method and supplemental oxygen between the groups. Shapiro-Wilk test for normality was used for the continuous outcomes. Paired t-tests or Wilcoxon singed-rank

tests were used to assess changes in growth velocity and feeding therapy characteristics between time-1 and time-2. Two sample t-tests or Wilcoxon rank-sum tests were used to compare these continuous outcomes between conventional and study groups. Median (interquartile range [IQR]), mean (SD), or % was reported, unless stated otherwise.  $P$  values  $<0.05$  were considered statistically significant, and SAS version 9.4 (SAS, Inc, an IBM Company, Chicago, IL) was used.

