## STUDY OUTCOMES

### Primary and Secondary Clinical Outcomes

The clinically meaningful primary and secondary outcomes did not differ significantly between groups (**Table 2**). I-GERQ-R scores for study and conventional groups are shown (**Fig 2**). At inception: positive I-GERQ-R was 19/35 (54%) in the conventional group vs 24/37 (65%) in the study group,  $p=0.36$ . At Time-2: positive I-GERQ-R prevalence was 9/31 (29%) in the conventional group vs 13/34 (38%) in the study group,  $p=0.43$ . In the study group vs conventional group, respectively: a) primary outcome achieved in 33% (95% CI, 19% - 49%) vs 44% (95% CI, 28% - 62%) ( $p=0.28$ ), b) secondary outcomes: independent oral feeding in 65% (95% CI, 48% - 80%) vs 77% (95% CI, 60% - 90%),  $p=0.26$ ,  $\geq 6$ -point I-GERQ-R decrease in 38% (95% CI, 22% - 56%) vs 35% (95% CI, 19% - 55%),  $p=0.82$ , length of stay was 98 [81-132] days vs 108 [83-125] days,  $p=0.89$ , and oxygen requirement at discharge in 19% (95% CI, 8% - 35%) vs 26% (95% CI, 13% - 43%),  $p=0.49$ . There were no significant differences in growth metrics (all  $p>0.05$ ) or developmental scores at 2 years (all  $p>0.05$ ). Feeding outcomes or I-GERQ-R scores did not significantly differ between conventional vs study groups based on feeding method at inception (**Table 3**). Individual I-GERQ-R questions relating to vomiting, regurgitation, and crying (i.e. frequency of emesis, volume of emesis, symptoms with emesis, and crying more than usual in the

past week) had no differences ( $P>0.05$ ) within the group or between the groups across maturation for these individual symptoms, except for symptoms with emesis (never: rarely: sometimes: often: always, %) was 16:16:42:19:6 for conventional group at Time-1 vs 18:18:29:0:35 for study group at Time-1,  $p < 0.01$ .

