### **DISCUSSION**

In this RCT, while controlling for birth gestation and severity of acidity, we compared the effectiveness of acid suppression with or without a systematic feeding modification bundle in modifying feeding outcomes and I-GERQ-R scores. We found no differences in our *a priori* primary outcome or pre-assigned secondary outcomes. Important clinical and research implications can be noted despite the non-superiority of the feeding bundle.

Diagnostic conundrums and management issues with GERD in the NICU setting persist. Prior studies (8, 19, 20) used perceived clinical symptoms as a basis for acid-suppression, but studies have shown lack of benefit on symptom improvement (35, 36). Recent work by us (6, 21, 22), suggests that such symptoms are often due to pharyngo-esophageal provocation or cross-systems activation of reflexes, and can occur during non-acid events or swallowing events, or

during transient relaxation of lower esophageal sphincter (30). However, the inability to handle the refluxate determines the ‘troublesomeness of the symptoms’ rather than the esophageal acid exposure. Clinical practice varies when pathophysiological reasoning is not commonly applied. Clinical practices can have unintended consequences (1, 37-40) resulting from acid suppression, undernutrition, delays with feeding milestones, decisional conflicts, discharge outcomes and prolonged hospitalization, all of which can escalate burden (9, 27).

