is justifiable in future trials, as nearly 40% of infants are in this severe range, and it is possible to study such a group in larger clinical trials based on pH and impedance criteria, while employing placebo for equipoise. Since time-limited PPI therapy concurrent with feeding strategies was neither shown to be beneficial or associated with adverse effects, we believe that, it is safe to include a completely untreated placebo group in future trials that enroll patients with objectively determined acid-GERD. 2) The management strategies were tightly regulated, as were feeding and testing guidelines, and the treatment was uniformly delivered across the two groups. The patient population was homogeneous and constituted a fair representation from the convalescing NICU population. In addition, the randomized controlled allocation accounted for premature or full-term birth, and the indeterminate or determinate acid-GERD per ARI. Furthermore, the prevalence of oxygen requirement or tube feeding at discharge was not different between groups. 3) Our study trial has many elements of objectivity. Determination of I-GERQ-R and ARI, as well as monitoring feeding methods during the trial are strengths. Thirty-six percent of those with aerodigestive and or cardiorespiratory symptoms perceived by their clinicians to be due to GERD prior to trial consent, were not randomized and were also never treated with a PPI as the esophageal acid exposure was normal (ARI < 3%). In a purely symptom-based clinical trial, all those 688 infants screened would have likely been treated for presumed GERD. In the current study, only those that had true ARI exposure have been randomized and treated. Therefore, the symptom-based approach alone is not the solution to diagnose and treat GERD. Interestingly, perception of symptoms (IGERQR scores) decreased across time regardless of treatment group allocations (**Fig 2**). These findings strongly support maturational effect. As both groups were treated with PPI, placebo-included RCTs are needed to determine if maturation alone will improve objectively determined acid- and non-acid-GERD. 4) Absence of pH-impedance testing to confirm true acid-GERD prior

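### The protocol ranks none of its three analyses as primary, the planned feeding-route-adjusted model is not reported, and the stated control for gestation and ARI was stratified randomisation only

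*Combined protocol and SAP*

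**What the plan says.** **Report.** Statistical Methods assign the chi-square to the primary outcome: success rates were "compared using chi-square test between the conventional and study groups (primary outcomes"), by intention to treat and as treated. Table 2 gives 16/36 (44%) conventional and 13/40 (33%) study, p=0.28.

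**Protocol.** Section 3.3 names three analyses:
- a chi-square test of success proportions, under Sample Size Determination;
- logistic regression for success, with oral versus tube feeding as an example of a covariate to include;
- a linear mixed model for symptom scores, which it labels the primary endpoints of Aim 1, as does section 2.2.

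Section 4.0 makes binary success the primary endpoint. No section says which analysis is primary.

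**Gestation and ARI.** Randomisation was "stratified 1:1 ratio by ARI severity" and by preterm or full-term birth. The Key Points present the result as obtained "when controlling for preterm or full-term birth and severity of esophageal acid reflux index". The Introduction states the objective "while controlling for gestational maturity (pre-term or full-term at birth) and severity of esophageal ARI". The Discussion says the arms were compared "while controlling for birth gestation and severity of acidity", and later that "the randomized controlled allocation accounted for premature or full-term birth, and the indeterminate or determinate acid-GERD per ARI".

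**Feeding route.** Under Outcome Measures and section 4.0, an infant still moving to oral feeds succeeds on full oral feeding or a 6-point score fall. For an infant already on full oral feeds, "success was determined if full oral feeds were maintained plus a" 6-point fall. The results text says "Feeding outcomes or I-GERQ-R scores did not significantly differ between conventional vs study groups based on feeding method at inception", citing Table 3, which compares the arms separately within each route.

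**The concern.** A plan that lists several analyses without ranking them gives no fixed point against which to check the reported one. Here the report carries the simplest of the three and says nothing about the logistic model that the protocol said would assess success. None of the eight entries in the protocol's revision history records such a change.

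Route is the obvious covariate. It is known at baseline and decides whether success needs one component or both, so success should be easier for tube-fed infants. It was not a randomisation stratum, so chance imbalance in route adds noise to the crude comparison.

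The control statements raise a separate problem. A reader of the Key Points would expect an estimate adjusted for gestation and ARI, and the report contains none.

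**Working it through.** **1. Reported test.** Inputs from Table 2: 16/36 and 13/40, pooled rate 29/76 = 0.3816.
z = (0.325 - 0.444) / sqrt[0.3816 x 0.6184 x (1/36 + 1/40)] = -0.1194 / 0.1116 = -1.07, two-sided p = 0.2845.
This matches the reported 0.28, so the test is unadjusted, two-sided and uncorrected (continuity-corrected p is 0.40, Fisher's exact 0.35). The risk difference is -11.9 points (95% CI -33.7 to 9.8).

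**2. Sizing test.** Inputs from section 3.3: 40% against 67% (40 + 27), 50 per arm, one-sided 0.025.
0.27 / sqrt[(0.40 x 0.60 + 0.67 x 0.33)/50] - 1.96 = 2.81 - 1.96 = 0.85, power 80.3%. With pooled variance it is 78.1%. The stated 80% reproduces, with the chi-square as the sizing test.

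**3. Search for an adjusted result.** There is none in Statistical Methods, the outcomes text, Table 2 or Table 3. Table 3 has only unadjusted comparisons within route (tube-fed p=0.39, orally fed p=1.0).

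**4. Size of the route effect.** Row labels in Table 3 are displaced in the text supplied. I placed the values by the identity oral + score - both = either: 11 + 7 - 4 = 14 and 7 + 8 - 2 = 13. Applying the stated success rule, with unscored infants as failures:
- tube-fed: 14/18 conventional, 13/20 study, together 27/38 = 71%;
- orally fed: 4/17 and 5/17, together 9/34 = 26% (9/28 = 32% among scored infants).

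The gap is 39 to 45 points. But the totals are 14 + 4 = 18 and 13 + 5 = 18, against 16 and 13 in Table 2. Suppose instead that Table 2's total of 29 is kept with Table 1's denominators (39 tube-fed, 37 orally fed). With 9 orally fed successes the gap is 20/39 - 9/37 = 27 points; with 27 tube-fed successes it is 27/39 - 2/37 = 64 points.

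**5. Effect on power.** Assumptions: control rates by route as shown, half the infants tube-fed, 50 per arm, 40% against 67% overall, one-sided 0.025. Simulation with 300,000 runs per setting; pooled z (crude) against Cochran-Mantel-Haenszel by route.

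| Control tube/oral (%) | Effect pattern | Route balanced: crude, stratified | Route left to chance: crude, stratified |
|---|---|---|---|
| 65/15 | common odds ratio | 0.831, 0.889 | 0.799, 0.886 |
| 60/20 | common odds ratio | 0.818, 0.849 | 0.798, 0.846 |
| 53.5/26.5 | common odds ratio | 0.808, 0.814 | 0.798, 0.808 |
| 50/30 | common odds ratio | 0.803, 0.804 | 0.798, 0.794 |
| 60/20 | mainly tube-fed (treated 95/39) | 0.835, 0.894 | 0.799, 0.889 |
| 60/20 | mainly orally fed (70/64) | 0.809, 0.811 | 0.799, 0.801 |
| 60/20 | orally fed only (60/74) | 0.810, 0.811 | 0.799, 0.787 |

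Route left to chance is the actual design. There the crude test's type I error is 0.026 at both 60/20 and 65/15, about nominal. It is conservative (0.0165 and 0.0120) only when route happens to be balanced.

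**6. Completed trial.** Table 2's successes can be divided by route in 17 x 14 = 238 ways (tube/oral denominators 18/18 conventional, 21/19 study). Over all of them:
- the stratified risk difference runs from -13.8 to -10.0 points;
- the route-adjusted odds ratio (study against conventional) runs from 0.20 to 0.61, two-sided p 0.07 to 0.30.

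The 0.20 extreme has no orally fed success in either arm, which Table 3 contradicts. The 18 splits that do not exceed Table 3's counts in any cell give 0.34 to 0.56, p 0.12 to 0.24. Table 3's own counts give 0.82 (95% CI 0.29 to 2.31), p=0.71. All of these odds ratios are below 1, so none favours the bundle.

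**The case against.** The strongest reply is that the report does name its primary analysis. Statistical Methods attach the chi-square to the primary outcome, Table 2 labels that result intention-to-treat, and the sample size rests on the same test. That stands. A reader might infer that no primary analysis was named anywhere, or that the test was picked after the data were seen. The documents support neither. The gap is that the protocol does not rank its three analyses and the report does not say why one of them is missing. The mixed model concerns a different variable, so it is an inconsistency in naming the endpoint rather than a rival test of success.

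It can also be said that stratified allocation is a form of control. The Introduction ties its phrase to the randomised assignment, and a later Discussion passage speaks of allocation. That is fair for the Introduction, and the first Discussion statement is ambiguous. The Key Points sentence, which describes the result itself, reads as an adjusted finding.

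A third reply is that adjustment is not free. This stands too. With route left to chance, stratifying loses 0.4 points at 50/30 and 1.2 points if the effect lies only in orally fed infants. Crossing route with ARI and gestation costs more. A simulation of that eight-stratum Mantel-Haenszel test, with ARI and gestation balanced and assumed not prognostic, went from 0.798 to 0.780 at 50/30 and from 0.797 to 0.766 with the effect in orally fed infants only. It still gained at 60/20 with a common odds ratio (0.801 to 0.834).

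**Conclusion.** The point holds as one of pre-specification and reporting. The protocol designates no primary analysis among three, the planned route-adjusted model is absent without explanation, and the stated control for gestation and ARI corresponds to stratified randomisation.

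The effect of route adjustment on power is about -1 to +9 points under assumed control rates. The larger gains need a strong route effect, and the prognostic strength of route cannot be fixed until Tables 2 and 3 agree. No loss from leaving out ARI or gestation can be shown, because no outcome counts by those strata are given.

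Two further inferences are not supported. The chi-square is not invalid: its type I error is about nominal in this design. Nor would adjustment for route rescue the bundle: neither Table 3's counts nor any division of Table 2's successes favours it, so the no-superiority conclusion does not change.

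**What to change.** **In the plan.** Name binary success as the primary endpoint and one primary analysis: logistic regression with main effects for feeding route at inception, ARI stratum and birth gestation, reported as a standardised risk difference. Do not use Mantel-Haenszel over all cross-classified strata, since only 8 of 76 infants are full-term (2 conventional, 6 study, from Table 1). Keep the chi-square as a sensitivity analysis and the symptom-score mixed model as secondary.

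**For the completed trial.**
1. Reconcile Table 3 (18 and 18 successes) with Table 2 (16 and 13).
2. Report the planned route-adjusted logistic model beside the chi-square.
3. Label any ARI and gestation terms post hoc, since the protocol's model does not name them.
4. Unless a result adjusted for gestation and ARI is reported, reword the Key Points, Introduction and Discussion to say that randomisation was stratified by those factors.

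**Cost.** No new data or infants, and a little more analysis. There is a possible power loss of about 1 point for route under some effect patterns. The logistic model with added ARI and gestation main effects was not simulated, so its cost is not quantified here.

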*Salient features of our study include:* 1) Allocations were unbiased and appropriately distributed between groups. 2) Among those presenting with GERD symptoms at inception, about 36% of infants had normal esophageal acid exposure, while 40% had abnormal acid exposure, and the rest in the indeterminate range. 3) The study bundle was not superior to acid suppression alone in improving primary outcomes or secondary outcomes. 4) Restricted feeding volume, body positions (intra- and post-prandial), oral or gavage feeding methods, supplemental oxygen, birth gestation and postnatal maturation did not influence the primary or secondary outcomes. 5) Reliability of compliance among those discharged was based on parental trust and available information. 6) There were no reported adverse events. No differences in long term developmental outcomes or economic burden measures, such as, LOHS, feeding methods and respiratory support at discharge were noted. 7) Symptom scores (I-GERQ-R) were significantly lower in both groups, suggesting that maturation may play a role in symptom modification, and not the bundled approaches. 8) Feeding outcomes improved in both groups.

*GMT Trial strengths and clinical implications are several:* 1) Random allocation, study design and protocol adherence were robust and rigorous. Although our strict inclusion criteria may have led to lower eligibility, our approach resulted in identifying infants carefully with true ARI as a marker of esophageal acid exposure. Objective determination of GERD based on ARI >7%

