**FIGURE 1.**

**Figure 1. Study Enrollment and Randomization.** Depicted is the CONSORT diagram describing participant flow and randomization into the conventional or study bundles, and subjects analyzed for outcomes.

## FIGURE 2

**Figure 2. I-GERQ-R Outcomes.** Depicted is a combination plot by group (boxplots) and individual I-GERQ-R scores (black line represents median). Note that parent perception scores (I-GERQ-R) significantly decreased in both groups at Time-2.

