### 3.3 Statistical procedures

- Statistical Analyses:
  - Aim I: Outcomes: We will test the hypothesis that the innovative feeding strategy provided over 4 wks is more effective than standard therapy for the acquisition of safe feeding skills by improved symptom scores (Primary), improved individual I-GERQ-R measures, growth measures, reduced lengths of stay and resource utilization (Secondary). Linear mixed models will be used to study the associations between the primary endpoints for Aim 1 (symptom scores) and treatment, and trend across time. The interaction term “group x time” will be included in the model to study whether the two treatment groups have different “behavior” across time. Confounder variables, such as medications, feeding position or volume, will be included in the models. Logistic regression models will be used to assess success of the treatment vs. standard of care. Also, potential confounders (e.g. feeding method: oral vs. tube) will be included and studied in these models. Holm’s method will be used to adjust for multiple comparisons (150). All the secondary variables listed above, will be analyzed using either linear mixed models or logistic regression models. Model goodness of fit tests and residual analyses will be performed to assess the models. Interaction terms and potential confounder variables will be included.
  - Aim II: Mechanistic Hypothesis: We will test the hypothesis that the sensory-motor characteristics of aerodigestive reflexes evoked with induced esophageal stimulation or upon spontaneous esophageal provocation as in GER, improve in the innovative therapy group with regards to: sensory thresholds, response latency and duration, frequency and magnitude of reflexes, TLESRs, spatial-temporal-physical- chemical characteristics of GER events with associated symptom indices. Based on the preliminary data, we will have at least 80% power to detect the above differences of pre and post therapy between the two groups. Linear mixed models or logistic regression models (depending on the nature of the outcome variable) will be used to study the associations of interest within sensory motor components of aerodigestive reflexes within and between study groups and their outcomes. Potential confounders as well as interaction between groups and type of infusion will be included in the models. We have utilized similar models previously. Correlation between symptom indices (SI, SSI, SAP) and reflexes will be calculated.

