  - Every patient who had been randomized will be included in the analysis. If a patient drops off before end of study and no symptom score has been measured, we will treat the patient as a failure. Beside the intention to treat analysis, we will also perform the analysis with only those patients that complete the study. Linear mixed models will be used to study the associations between the primary endpoints for Aim 1 (symptom scores) and treatment, and trend across time. The interaction term “group x time” will be included in the model to study whether the two treatment groups have different “behavior” across time. Confounder variables, such as medications, feeding position or volume, will be included in the models. Logistic regression models will be used to assess success of the treatment vs. standard of care. Also, potential confounders (e.g. feeding method: oral vs. tube) will be included and studied in these models. Holm's method will be used to adjust for multiple comparisons. All the secondary variables listed above, will be analyzed using either linear mixed models or logistic regression models. Model goodness of fit tests and residual analyses will be performed to assess the models. Interaction terms and potential confounder variables will be included.
  - The proposed projects will focus on esophageal provoking stimuli in designing multi-faceted innovative therapies, that will be studied in a prospective single center randomized blinded controlled trial. The pH- Impedance data with associated symptom indices will be analyzed. This trial will advance our knowledge of GER and GERD in infants. These studies will likely mandate the development of infant-specific diagnostic and treatment paradigms to manage not only GERD but also other diseases where GERD is a co-morbidity.

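### The planned group x time model for I-GERQ-R and the other planned models are replaced by unadjusted tests without disclosure, so the visible text gives no between-arm estimate of the change in symptom score.

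*Combined protocol and SAP*

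**What the plan says.** **The plan (protocol section 3.3, under Statistical Analyses and again under Intention to treat analysis).** Linear mixed models are to relate "the primary endpoints for Aim 1 (symptom scores) and treatment, and trend across time". A group x time term "will be included in the model to study whether the two treatment groups have different" courses over time. For the binary endpoint, "Logistic regression models will be used to assess success of the treatment vs. standard of care". For the rest, "All the secondary variables listed above, will be analyzed using either linear mixed models or logistic regression models". Holm's "method will be used to adjust for multiple comparisons". Medications and feeding position or volume are named as confounders in the mixed model, and feeding method as one in the logistic model.

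**The report (Statistical Methods).** Success and the other categorical outcomes are compared by chi-square or Fisher's exact test. Changes in growth velocity and feeding characteristics are assessed within patients by paired t or signed-rank tests, and those same continuous outcomes are compared between arms by "Two sample t-tests or Wilcoxon rank-sum" tests. No regression model, covariate or Holm step is described, and the threshold is p<0.05 throughout.

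**What is said about the score.** The Figure 2 caption states that scores "significantly decreased in both groups at Time-2". The Discussion repeats that "Symptom scores (I-GERQ-R) were significantly lower in both groups" and reads this as pointing to maturation rather than the bundle. The Conclusion calls the support for maturation strong and says the feeding modification plays no part in reducing reflux-type symptoms.

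**What is said about adjustment and about changes.** The Key Points and the opening of the Discussion say the comparison controlled for birth gestation and acid reflux index (ARI) severity. Study Oversight says important changes to methods are listed in Supplement 1. The IRB revision history has eight entries. The last adds a biostatistician to the staff; none changes the analysis.

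**The concern.** Two significant within-arm falls do not compare the arms. Both arms can fall significantly while one falls further, and both can fall equally. The group x time term separates these cases. It was planned, and the scores were collected. Without it, the reader has no estimate of how much more or less the score fell with the bundle, and no interval showing which differences are excluded. The text nonetheless moves from falls in both arms to a statement that the bundle has no role.

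The departure is not confined to secondary outcomes. Section 3.3 attaches the group x time model to what it calls the Aim 1 primary endpoint, and the planned logistic model for success and the Holm adjustment are missing as well. The statement that results controlled for birth gestation and ARI severity describes the stratified randomisation, but not any analysis that is described.

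**Working it through.** **1. Are the reported binary results crude?** Inputs are the counts in Table 2 and the Study Outcomes text (conventional vs study). The test is Pearson chi-square without continuity correction, z = difference / sqrt[p(1-p)(1/n1 + 1/n2)] with p pooled.

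| Outcome | Counts | Reported p | Recomputed p |
|---|---|---|---|
| Primary success | 16/36 vs 13/40 | 0.28 | 0.284 |
| Fall of at least 6 points | 11/31 vs 13/34 | 0.82 | 0.818 |
| Oxygen at discharge | 9/35 vs 7/37 | 0.49 | 0.488 |
| Positive score, inception | 19/35 vs 24/37 | 0.36 | 0.360 |
| Positive score, Time-2 | 9/31 vs 13/34 | 0.43 | 0.434 |

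Example, 6-point fall: p = 24/65 = 0.369; SE = sqrt(0.369 x 0.631) x sqrt(1/31 + 1/34) = 0.483 x 0.248 = 0.120; z = 0.0275/0.120 = 0.23. All five match. Continuity-corrected and Fisher versions do not (primary success: 0.40 and 0.35). These are unadjusted comparisons.

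**2. What the responder comparison excludes.** Difference = 13/34 - 11/31 = 0.382 - 0.355 = +2.8 points. Unpooled SE = sqrt(0.382 x 0.618/34 + 0.355 x 0.645/31) = 0.120. The 95% CI is 2.8 +/- 1.96 x 12.0 = -20.7 to +26.2 points.

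**3. A rough stand-in for group x time.** The visible text gives no mean or SD of the score by arm and visit, so the planned model cannot be run. The positive/negative counts give a crude version.
- Conventional: 54.3% to 29.0%, a change of -25.3 points. Study: 64.9% to 38.2%, a change of -26.6. Difference in change: -1.4 (from unrounded values).
- Odds ratios, Time-2 over inception: conventional (9/22)/(19/16) = 0.344; study (13/21)/(24/13) = 0.335. Ratio of odds ratios = 0.97.
- Treating visits as independent, the variance of the log ratio is the sum of the eight reciprocal counts, 0.515, so SE = 0.718 and the 95% CI is 0.24 to 3.97. Lowering the variance for an assumed within-infant correlation gives 0.30 to 3.16 at 0.3 and 0.36 to 2.64 at 0.5.

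The estimate is near null, and the interval is wide in every case.

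**4. How much information dichotomising gives up.** The documents give none of these inputs, so all are assumptions: SD 6 at each visit, mean fall 3.5 in the conventional arm, two-sided 5%, correlation r between visits of 0.3, 0.5 or 0.7. The sample is the 31 and 34 infants actually scored.
- Change score, which is what group x time reduces to with two visits: SD = 6 x sqrt(2(1-r)) = 7.10, 6.00, 4.65; SE = SD x 0.248 = 1.76, 1.49, 1.15.
- Baseline-adjusted score (ANCOVA): SD = 6 x sqrt(1-r^2) = 5.72, 5.20, 4.28; SE = 1.42, 1.29, 1.06.
- Responder rate = P(fall of at least 6), from a normal change score. For a 4-point effect: 36% vs 58%, 34% vs 60%, 30% vs 63%.

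| Power, 4-point effect | r = 0.3 | r = 0.5 | r = 0.7 |
|---|---|---|---|
| Responder chi-square | 42% | 56% | 77% |
| Group x time (change score) | 60% | 76% | 92% |
| ANCOVA | 79% | 86% | 96% |

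These are simulation results; closed-form power agrees within about one point. For a 2-point effect no method exceeds about 45%.

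**The case against.** The strongest reply is that between-arm evidence on symptoms exists and points one way. The 6-point fall is measured from each infant's own baseline, is the documents' stated threshold for clinical improvement, and is a component of the protocol endpoint. Positive-score prevalence is compared at both visits, single items are compared between arms, and Table 3 gives responders by feeding method at inception. The non-superiority conclusion rests on these comparisons, not on within-arm p-values. This stands. What it does not supply is an effect estimate on the score, with an interval, from the planned analysis.

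Five stronger readings are tempting and go beyond the documents:
- **The paired and two-sample tests were the I-GERQ-R tests.** Statistical Methods ties them to growth and feeding measures; the test behind the Figure 2 statement is not named.
- **The group x time test was never done or reported anywhere.** Figure 2 is not available here. Only its absence from the visible text can be stated.
- **The responder test ignores baseline.** It uses baseline through the change; it is dichotomised and unadjusted.
- **The full gap between the responder test and ANCOVA is the cost of leaving the plan.** Section 3.3 plans group x time and does not mention baseline as a covariate. At r = 0.3 the loss against the plan is 60 - 42 = 18 points; the further 19 points up to ANCOVA would be an improvement on the plan.
- **The planned model would overturn the result.** The crude interaction gives no sign of that.

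The maturation claim also has a larger gap, the lack of an arm without PPI. The Discussion acknowledges it, and a group x time test would not close it.

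**Conclusion.** The concern holds as an undisclosed departure from the planned analysis and a missing between-arm estimate. Matching p-values show that the five checked binary results are crude; the absence of models for continuous outcomes rests on the Statistical Methods text. No described analysis supports the statement that birth gestation and ARI severity were controlled for.

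The effect on the conclusion is limited. Failure to show superiority would probably survive the planned model. The claim that the bundle has no role in symptoms is not supported: the responder interval reaches about 21 points in one direction and 26 in the other. The power figures are illustrations that depend on the assumed SD, mean fall, effect and correlation. They show that the planned contrast would have been clearly more sensitive to a moderate effect, and that neither approach could settle a small one.

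**What to change.** - Report the between-arm difference in I-GERQ-R change with its 95% CI from the planned group x time model, and give mean and SD by arm and visit.
- As a stated improvement on the plan, add a version adjusted for baseline score and the randomisation strata: ARI category and, where numbers allow, term or preterm birth. Only 8 of 76 infants were term (2 conventional, 6 study), so the second factor may have to be dropped for some outcomes.
- Leave feeding position and volume out of the main model, although section 3.3 lists them as confounders. The bundle sets them, so adjusting for them would remove part of the effect being estimated.
- Use the planned logistic model for success and the planned models for secondary outcomes, with Holm adjustment. Keep exact tests where events are rare, such as exclusive tube feeding at discharge (4 infants).
- State in the methods that the analysis departs from section 3.3, and why. Either adjust for birth gestation and ARI severity or say they were stratification factors only.
- Do not infer absence of a bundle effect from within-arm p-values, and limit the Conclusion to what the interval supports.

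The cost is a few model runs on data already collected and some rewording.
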